Introduction of a maturation function did not show any significant improvement in the model based on the current data. As maturation is known to exist, these results suggest that the available data are insufficient to estimate the effect of age on the PK of ETR. Therefore, additional data in younger patients is needed (Cohorts II and III).

Given the uncertainties around maturation of CYP metabolism in subjects aged <1 year, some additional precautions are taken for Cohort III:

- 6 months to < 1 year: the dose (in mg/kg) is reduced by 25% compared to what the model suggests to adjust for possible ongoing maturation of enzymatic metabolism (30)
- 2 months to < 6 months: subjects in this age group will only be included once there are available data on subjects aged 6 months to 1 year

Safety of the weight-based dosing in the younger participants is anticipated to be acceptable based on the safety data collected so far among subjects in Cohorts I and II. The latter was opened 30 October 2015 and, based on input from participating sites in late 2015, the expectation is that there will be at least 2 and likely 6 participants already enrolled in Cohort II by the time of release of Version 5.0. There are adequate safeguards included in the protocol, which include:

- Intensive PK evaluation with individual dose adjustment if needed and continuous safety monitoring on an individual level;
- Close monitoring of PK data and continuous safety monitoring on a cohort level;
- Additional safety monitoring rules for first 6 patients entering cohorts II and III combined.

In conclusion, the added scientific value of the collected data -and the precautions taken to ensure safety and efficacy of the compound in this age group- justifies an early enrollment of Cohort III.

Other Available Data

In a Spanish cohort of five children (5 to 12 years old) and 18 adolescents (13 to 18 years old) of whom 22 had a history of NNRTI-based CART failure with proven genotypic NNRTI resistance mutations, salvage regimens including ETR at 5.2 mg/kg BID (for children) and 200 mg BID (for adolescents) and (in 21 of the patients) OBR with at least 2 active agents, 87% achieved HIV-1 RNA< 400 copies/mL and 78% achieved HIV-1 RNA< 50 copies/mL by 8 months. Mild (3 adolescents) or moderate (2 adolescents) rash was observed only in adolescents but not in children, and therapy was otherwise well tolerated (31).

Table 5. Adverse Events Summary (Adult Studies Phase IIb /III Pooled Analysis)

AEs during treatment period n (%)	Week 48 Placebo DUET N = 604	Week 48 ETR DUET N = 599	ETR Selected Dose N = 1043	All ETR N = 1223
Treatment duration (weeks), Median (range)	51.0 (3 - 80)	52.3 (2 - 85)	51.7 (0 - 271)	52.3 (0 - 271)
Subject years of exposure	556.8	583.4	1125.1	1476.2
Any AE	580 (96.0)	575 (96.0)	990 (94.9)	1164 (95.2)
Any Grade 1 or 2 AE	573 (94.9)	564 (94.2)	973 (93.3)	1143 (93.5)
Grade 1	512 (84.8)	511 (85.3)	877 (84.1)	1040 (85.0)
Grade 2	425 (70.4)	445 (74.3)	751 (72.0)	888 (72.6)
Any Grade 3 or 4 AE	211 (34.9)	199 (33.2)	347 (33.3)	434 (35.5)
Grade 3	190 (31.5)	177 (29.5)	311 (29.8)	387 (31.6)
Grade 4	64 (10.6)	59 (9.8)	106 (10.2)	135 (11.0)
Treatment-related AE ^a	285 (47.2)	320 (53.4)	557 (53.4)	671 (54.9)
Death	20 (3.3)	12 (2.0)	21 (2.0)	26 (2.1)
Any SAE	141 (23.3)	118 (19.7)	205 (19.7)	254 (20.8)
AE leading to temporary stop	57 (9.4)	64 (10.7)	131 (12.6)	161 (13.2)
AE leading to permanent stop	34 (5.6)	43 (7.2)	101 (9.7)	127 (10.4)
Most Common AEs^b				
Diarrhea	142 (23.5)	108 (18.0)	202 (19.4)	266 (21.7)
Nausea	77 (12.7)	89 (14.9)	175 (16.8)	214 (17.5)
Headache	77 (12.7)	65 (10.9)	127 (12.2)	168 (13.7)
Injection site reaction	75 (12.4)	63 (10.5)	109 (10.5)	144 (11.8)
Fatigue	57 (9.4)	48 (8.0)	107 (10.3)	140 (11.4)
Nasopharyngitis	63 (10.4)	66 (11.0)	111 (10.6)	133 (10.9)
Upper respiratory tract infection	56 (9.3)	44 (7.3)	94 (9.0)	123 (10.1)
AEs of interest				
Any skin event of interest	110 (18.2)	159 (26.5)	288 (27.6)	353 (28.9) ^c
Rash (any type)	66 (10.9)	115 (19.2)	207 (19.8)	249 (20.4)
Any neuropsychiatric event of interest	205 (33.9)	181 (30.2)	338 (32.4)	427 (34.9) ^d
Nervous system events of interest	119 (19.7)	103 (17.2)	191 (18.3)	249 (20.4)
Psychiatric events	118 (19.5)	100 (16.7)	196 (18.8)	248 (20.3)
Any hepatic event	37 (6.1)	39 (6.5)	86 (8.2)	103 (8.4)

Any cardiac event	44 (7.3)	42 (7.0)	92 (8.8)	124 (10.1)
Coronary artery disorders	8 (1.3)	11 (1.8)	16 (1.5)	28 (2.3)
Any pancreatic event	27 (4.5)	24 (4.0)	38 (3.6)	51 (4.2)
Any bleeding event	39 (6.5)	33 (5.5)	59 (5.7)	76 (6.2)

N: number of subjects; n: number of subjects with observations

^a defined as possibly, probably or very likely related to treatment in the opinion of the investigator

^b > 10% of subjects in the All ETR group

^c Of the total skin rashes, 1.5 % were Grade 3; there were no Grade 4 skin rashes

^d Of neuropsychiatric events, 0.7% were Grade 3; 0.2% (1 patient had a Grade 4, and it was a suicide).

Additional Safety Data

Safety data derived from pooling of the results of 1,043 adult HIV-1-infected treatment-experienced subjects enrolled in the Phase III trial indicated that ETR is generally safe and well tolerated. The most common AEs reported during ETR treatment with the selected dose were rash (any type, 16.9%; Grade 2 to 4 rash 9%), diarrhea (any Grade 1: 9.4%; Grade 2 to 4: 5.2%), nausea (any Grade, 13.9%), and headache (Grade 1: 2.2%; Grade 2 to 4: 2.7%).

With the exception of rash, the incidence of AEs and laboratory abnormalities were generally comparable to placebo. Table 5 describes these results.

A recent double-blind placebo-controlled trial of ETR 400 mg QD versus EFV in HIV-infected adults, naïve to ART, compared neuropsychiatric side effects in the two arms. At week 12, 16.5% of ETR treated subjects reported at least one grade 1 to 4 treatment related neuropsychiatric AE, compared to 46.2% in the EFV treated subjects; for grade 2 to 4 AEs, the incidence was 5.1% in the ETR arm and 16.7% in the EFV arm (32).

Twenty-six subjects (2.1%) died during the study while on ETR; 25 of which were judged not, or unlikely, related to ETR therapy. One death, due to myocardial infarction with cardio respiratory failure, in a subject with risk factors for premature coronary artery disease, was considered possibly related to ETR therapy (18).

The rashes tended to be mild to moderate; they usually occurred in the second week of therapy, and resolved within 1 to 2 weeks on continued therapy. In the adult phase III trials, the cumulative incidence of Grade 3 and 4 rashes was 1.3% for subjects on ETR and 0.2% for those on placebo. A total of 2% of subjects discontinued study due to rash. There were no cases of Stevens Johnson Syndrome (SJS) or toxic epidermal necrolysis (TEN) reported due to ETR in any of the Phase IIb/III studies (18).

In August of 2009, the FDA issued a warning to physicians, related to the occurrence of severe, potentially life threatening, and fatal skin rashes (erythema multiforme, SJS and TEN) linked to ETR use during the post marketing period. Prescribing information has been updated to reflect this information. The rate of SJS and TEN was < 0.01% each. The hypersensitivity reactions manifested as rash along with constitutional findings. At times, evidence of impending organ failure existed. The current recommendation is to stop ETR at the onset of severe skin rash, with careful clinical monitoring (13).

As of February 12th, 2016, fourteen participants between the ages of 2 to 6 years have been

enrolled into P1090. To date, adverse events have been primarily unrelated to study product; none raised concerns regarding the safety of ETR in this population. Specifically, there has been no reported skin rashes related to study med, nor any safety events related to EKGs obtained on the day of pharmacokinetic testing.

1.4 Rationale

There is increasing use of NNRTI-based regimens as initial therapy for HIV-1 infected children, especially in areas where HIV-1 exposed newborns receive NVP as part of PMTCT regimens and/or daily NVP for prevention of breastfeeding transmission (33). Though NNRTI-based CART regimens are effective, first generation NNRTI agents have a low genetic barrier to the development of resistance.

As a result, there are an increasing number of treatment-experienced infected infants and children who have failed, or will fail, their initial regimen. The majority of these infants, at the time of virologic failure to a NNRTI based regimen, will have mutations associated with resistance to first generation NNRTIs (7). Similarly, a high percentage of infected infants exposed to NVP as a component of PMTCT regimens will harbor virus with NNRTI related resistance mutations.(3-7). Failure or intolerance of LPV/rtv based regimens, especially among infants and children with prior NNRTI exposure (as treatment or for PMTCT), leaves few or no alternative treatment options (7).

ETR, a second generation NNRTI, approved for adult use, has a higher genetic barrier to HIV drug resistance than EFV or NVP and retains activity against EFV and NVP drug resistant HIV-1 isolates harboring the K103N and Y181C mutations (9, 10). The drug dosing and tolerability have been established in adult registration studies. Skin rash was the main treatment-limiting significant adverse event. It was seen in up to 20% of subjects, with 1 to 2% of subjects showing Grade 3 or 4 severity (18). Phase I/II trials of ETR in children aged 6 to 17 years of age demonstrated acceptable safety and tolerability, and established suggested dosing for this age group (24). See Section 1.32.

We propose to investigate ETR, in combination with at least 2 active ARVs, one of which must be a boosted PI, for treatment experienced HIV-1 infected infants and children aged 2 months to < 6 years.

2.0 STUDY OBJECTIVES

2.1 Primary Objectives

- 2.11 To evaluate the steady state pharmacokinetics of ETR in combination with an OBR in HIV-infected children aged \geq 2 months to < 6 years.
- 2.12 To determine the safety and tolerability of ETR in combination with an OBR in children aged \geq 2 months to < 6 years, through 48 weeks of therapy.
- 2.13 To determine the appropriate dose of ETR in combination of an OBR for children aged \geq 2 months to < 6 years.

2.2 Secondary Objectives

- 2.21 To assess the antiretroviral activity of ETR containing regimens through 48 weeks of therapy.
- 2.22 To determine the immunological changes (change in CD4 percent and absolute count; CD4/CD8 ratio and percent) through 48 weeks of ETR therapy in combination with an OBR.
- 2.23 To determine changes in viral drug resistance during 48 weeks of ETR therapy in combination with an OBR.
- 2.24 To assess the relationship between ETR pharmacokinetics and the antiviral activity and safety of ETR containing regimens.
- 2.25 To explore the relationship between subject-specific gene CYP profile, sex, age, weight, race, HIV regimen (e.g., boosted PI) and HIV response markers and pharmacokinetics of ETR.

3.0 STUDY DESIGN

This is a Phase I/II, multicenter, open label 48 week study of ETR in combination with at least 2 active agents (a boosted PI and at least one additional active drug), for treatment experienced HIV-1-infected infants and children \geq 2 months to < 6 years separated by age into three cohorts.

The study will, in a sequential manner, accrue subjects for an initial dose finding intensive PK component for age related cohorts. It is expected that up to 50 subjects will be accrued, to yield data from at least 36 evaluable¹ subjects with a minimum of 12 subjects for each of the three cohorts, who were started on the final approved dose for that cohort. The total sample size will depend upon the number needed to complete the dose finding stage of the study, the number of subjects who discontinue the study and the number of subjects required for regulatory approval of ETR in these populations. Up to 18 subjects may be enrolled into Cohort I.

The P1090 core protocol team will be responsible for reviewing the PK and safety data and approving the dose selection for each full and mini-cohort. The P1090 core protocol team will consist of the protocol chair and co-chairs, clinical trials specialist, NIAID and NICHD Medical Officers, data manager, pharmacologists, pharmacist, statisticians and Janssen R&D representatives.

¹NOTE: For the Week 24 (or Week 48) analysis, evaluable will be defined as having been treated exclusively on the dose determined to be optimal for a given age cohort and having either completed 24 (or 48) weeks of exposure to the study drug or having been classified as a safety failure, due to a study drug related adverse event occurring during the first 24 (or 48) weeks of treatment.

This study is designed to determine the appropriate ETR dose for HIV-1-infected infants and children and to evaluate the PK, safety and tolerability of ETR in this population. ETR will be administered as 25 mg scored tablets and/or 100 mg tablets swallowed as a whole or dispersed in an appropriate liquid vehicle (see Section 5.2).

3.1 Description of Cohorts

Subjects will be stratified by age and will undergo viral phenotype and genotype evaluations as described in Table 6 below.

3.2 Optimized Background Regimen

As described in Table 6, OBR for treatment experienced subjects must consist of at least two active agents, a boosted PI and at least one additional active drug, in addition to ETR.

[figure not shown]
Prior to the enrollment visit (entry), the protocol team must be notified and approve the proposed OBR regimen. OBR should be based on clinical status, treatment history, resistance data as well as availability of dosing guidelines and appropriate pediatric formulations.

Table 6. Description of Cohorts

Cohort	Description of Subject	Drug Regimen	Phenotyping / Genotyping Information	Comments	Anticipated Accrual		
					Mini Cohort	To complete a full cohort	Total cohort size
I	≥ 2 year to < 6 years who are treatment experienced	ETR + OBR (1 active boosted PI+ at least 1 other active drug)	HIV genotype and phenotype assays should be performed in real time and results available prior to starting study drug	Subjects will be enrolled providing the phenotypic assay results indicate a ≤ 10 fold change in sensitivity to ETR	6	6	Up to 18
II	≥ 1 year to < 2 years who are treatment experienced	ETR + OBR (1 active boosted PI+ at least 1 other active drug)	HIV genotype and phenotype assays should be performed in real time and results available prior to starting study drug	Subjects will be enrolled providing the phenotypic assay results indicate a ≤ 10 fold change in sensitivity to ETR	6	6	12
III	≥ 2 months to < 1 year who are treatment experienced ¹	ETR + OBR (1 active boosted PI+ at least 1 other active drug)	HIV genotype and phenotype assays should be performed in real time and results available prior to starting study drug	Subjects will be enrolled providing the phenotypic assay results indicate a ≤ 10 fold change in sensitivity to ETR	6	6	12

1. Subjects below 6 months of age will only be enrolled upon availability of initial safety and PK data from subjects between 6 months and 1 year of age.

Figure 2: Algorithm for Cohort Management as of Version 5.0

The investigator-selected ARVs in the OBR will be used in doses that are specified in the individual package inserts. Brand name ARVs and generics with tentative approval from the US FDA may be prescribed. For a list of tentatively approved generics, please consult <http://www.fda.gov/InternationalPrograms/FDABeyondOurBordersForeignOffices/AsiaandAfrica/ucm119231.htm>

If the site intends to use study products not marketed in the United States, sites should consult the DAIDS SOP on “Use of Study Products Not Marketed in the United States” (Jun 24, 2011). It is the sites responsibility to ensure that they are in compliance with this policy. Please refer to <http://www.niaid.nih.gov/LabsAndResources/resources/DAIDSClinRsrch/Documents/NonFDAApprovedProducts.pdf>

Applicable procedures and treatment guidance based on package inserts of the selected ARVs should be respected. Proposed OBR regimens for individual subjects will need to be approved by the protocol team prior to the enrollment (entry) visit.

3.3 Mini-Cohorts

Under prior versions of the protocol, enrollment moved in a sequential manner, from the oldest cohort to the next youngest cohort (Cohort I → Cohort II). Upon release of Version 5.0, the team will consider opening Cohort III while the first mini-cohort of Cohort II may still be enrolling based on available PK and safety data to ongoing participants. Subjects below 6 months of age will only be enrolled upon availability of initial safety and PK data from subjects of at least 6 months of age and less than 1 year of age (see Figure 2 and Section 3.5).

All cohorts will begin with enrollment into an initial mini-cohort of 6 subjects. Intensive PK on initial dose will be performed on Day 14 (\pm 4 days) (to allow ETR levels to reach steady-state) and the mini-cohort will be followed for 4 weeks to assess safety.

For all cohorts, plasma concentrations of ETR will be assayed in real time (within two weeks of sample receipt) by the protocol specified IMPAACT pharmacology laboratory. After the sixth subject is enrolled, enrollment into that cohort will pause so that the pharmacokinetics (PK) and safety data can be analyzed. The safety criteria are described in Section 8.52 and PK criteria are described in Section 9.0.

The P1090 core protocol team will review the PK and safety results of each mini-cohort, and if acceptable, enrollment will resume, at that dose, to complete enrollment of the remaining 6 slots.

Subjects who pass screening but cannot enroll because the mini-cohort is filled, will join a waiting list and will be given first priority to enroll when the remaining six slots are opened for that cohort. NOTE: Screening labs must be repeated if the subject is on the waiting list for \geq 60 days.

In the rare event where the results of a single subject’s intensive PK are extremely low, AND the site clinician/protocol team strongly suspect non-adherence, an additional subject may be enrolled into the mini-cohort to replace the non-adherent subject. The non-adherent subject may remain on study and on study drug (ETR), if the site investigator agrees it is in the best interest of the subject, but this subject will not be considered for dose-finding or safety final analysis.

If the PK or safety monitoring results of the mini-cohort suggest that a higher or lower dose is needed, the new dose will be agreed upon by the P1090 core protocol team (upwards for inadequate PK values; downwards for safety failure, or high PK values). Up to 6 new subjects will be enrolled as a new mini-cohort, for PK and safety evaluation of the new dose.

Those enrolled in a failed mini-cohort, who had acceptable PK parameters, antiviral activity and safety can remain on the same dose without dose adjustment and will be followed on study. Subjects from the failed mini-cohort may be dose adjusted to the new dose, if feasible and the site investigator and/or protocol team believe this is in the best interest of the patient. Such subjects will have truncated intensive PK evaluation (3 samples: pre-dose and samples 2h and 3-5h after dosing) 7-14 days after the dose change, for safety considerations, but will not be considered towards the cohort pass/fail criteria.

Two out of six of the children from the mini-cohort who passed the safety criteria in Version 3.0 would be on the same dose chosen for the new weight-banding dosing strategy in Version 4.0. Consequently, the team agreed that those two participants could be included in considering the Cohort I mini-cohort under V4.0; only four additional participants would be needed to complete enrollment into that mini-cohort. In future mini-cohorts, if dose adjustments need to be made but subjects in the prior failed cohorts were on the same dose that will be evaluated in the new cohort, the PK and safety data for these subjects will be carried forward and counted towards the number of evaluable subjects on the final dose.

Those who need an individual dose adjustment (see Section 9.34 for management of individual dose adjustments), will have a repeat 12 hour intensive PK performed between Day 7 to 14 following their dose adjustment. Subjects who require a dose adjustment but decline to undergo repeat intensive PK (see Section 9.34 for management of individual dose adjustments) will have ETR therapy discontinued and best available therapy by their clinician will be initiated.

If a subject discontinues therapy for a non-ETR related toxicity reason (e.g., drug intolerance to an OBR agent) the subject will be replaced. Subjects discontinued due to ETR toxicity will NOT be replaced; rather, they will continue to be counted as failures. However, the safety data from the subjects who replace them for PK purposes will also be used when applying the safety guidelines

3.4 Full Cohorts

Once PK and safety criteria have been met for a full cohort, subjects will continue their treatment in the specific cohort at the selected dose. The safety criteria are described in Section 8.52. In order to meet the PK criteria, the geometric mean AUC_{12h} in the cohort must be within 60 to 150% of the geometric mean AUC_{12h} in adults (i.e. between 2713 and 6783 ng•h/mL). The recommended dose must be approved by the P1090 core protocol team. If, however, the selected dose for a full cohort does not meet the PK and safety criteria, the dose may be adjusted for the subjects already in the cohort (as described above) and additionally new subjects will be enrolled, if needed, to have (at least) 12 subjects in total on the new starting dose. The evaluation of PK and safety will then be repeated. If the starting dose is still not acceptable, the dose selection process will be repeated.

Subjects from the failed cohort may be dose-adjusted to the new dose if the site investigator and protocol team believes this is in the best interest of the subject. These subjects will have a truncated intensive PK evaluation (sampling at pre-dose and 2hr and 3-5h after dose).

Those subjects that require an individual dose adjustment for high or low AUCs (see Section

9.34 for management of individual dose adjustments), will have a repeat intensive PK evaluation 7-14 days following their dose adjustment.

Those subjects from a failed cohort who are not dose-adjusted to the new dose, but had acceptable PK parameters and antiviral activity and safety can remain on the same dose and will be followed on study.

Subjects who require a dose adjustment but refuse to undergo repeat intensive PK (see Section 9.34 for management of individual dose adjustments) will have ETR therapy discontinued and will be replaced (but will be followed on study but off study drug).

If full cohort data are inconclusive, the protocol team may decide to enroll additional subjects at the starting dose, and/or the P1090 Study Monitoring Committee (SMC) may be asked to review the data and advise the team.

As enrollment into each cohort continues, the study team will review the data via conference call at least monthly, to ensure that the stated PK and safety targets are acceptable.

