The overall safety and PK data of the first 6 subjects on a given cohort will be evaluated with respect to the guidelines specified in Section 8.512 and in Section 9.0 of the protocol. Once these subjects have passed both PK and safety criteria, 6 additional subjects will be accrued to complete each cohort (up to 12 additional subjects may be accrued to Cohort I). The full cohort must also pass the PK and safety criteria (see Section 8.513 and Section 9.0). If the mini or full cohort fails either the safety or the PK guidelines, then the starting dose will be adjusted in the appropriate direction, (upwards for inadequate PK values; downwards for safety failure), if this is feasible. Subjects in a cohort that failed PK or safety but were receiving the same dose as that recommended in the new dosing cohort will be included in PK and safety analysis of the new dose and additional new subjects will be enrolled as appropriate at the new dose in order to have a mini-cohort of 6 subjects treated with the new dose. An initial evaluation of safety and PK will be made on the basis of data from these subjects. The evaluation will proceed as described above. In the event that the mini- or full cohort fails the PK criteria before the cohort completes accrual, then safety will be evaluated on all available subjects to confirm that a dose increase is not contraindicated.

If the P1090 core protocol team judges a given subject's PK data to be unevaluable, the subject will be replaced for dose finding purposes. Note that the subject would be replaced for evaluating safety, as well as PK, criteria, since unevaluable PK data would reflect uncertainty about appropriate exposure to the study medication.

The study accrual is designed to yield at least 36 evaluable subjects for the Week 24 (and 48) safety analyses, which analyses will occur when the last subject of the last cohort has reached week 24 (or Week 48). For these safety analyses, "evaluable" will be defined as having been treated exclusively on the dose determined to be optimal for a given age cohort and having either completed 24 (or 48) weeks of exposure to the study drug or having been classified as a safety failure, due to a study drug related adverse event

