8.51 Safety Guidelines

8.511 Evaluation of the Starting Doses During the Dose-Finding Stage

The attribution of relationship of serious adverse events to study drug for the purposes of employing the start, stop and pause rules specified below will be by consensus among the site investigator, the protocol team and the DAIDS medical officers. If unanimous agreement between them cannot be established, the relevant data will be reviewed by the independent Study Monitoring Committee as described above, which will make the final judgment concerning the relationship between study drug and the adverse event. Within this committee the decision will be determined by the majority opinion of this study's independent Study Monitoring Committee clinicians.

Gradation of relationship will use the following terminology:

- Not related
- Probably not related
- Possibly related
- Probably related
- Definitely related

An event judged to be at least possibly related to the study treatment will be considered to be a Suspected Adverse Drug Reaction (SADR) for purposes of the dose finding algorithm which follows.

8.512 First Six Subjects Started at a Given Dose Level in Each Cohort

For each study cohort (Cohort I, Cohorts II & III combined), the frequency of adverse reactions to the starting dose of the study medication will be evaluated on the first 6 subjects. The data will extend to the week 4 visit for subjects not requiring dose adjustment or until the visit on which the dose is adjusted, as described above. Further accrual into this cohort will be contingent upon meeting the following safety guidelines:

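### After a full-cohort failure, Protocol Section 3.4 fills the new dose to 12 children before re-evaluation, while Section 8.1 requires an evaluation at six first

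*Protocol*

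**What the plan says.** The protocol describes what follows a full-cohort failure in two places.

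- **Section 3.4.** The first step is that "the dose may be adjusted for the subjects already in the cohort (as described above"). Then "new subjects will be enrolled, if needed, to have (at least) 12 subjects in total on the new starting dose". Then: "The evaluation of PK and safety will then be repeated". No evaluation at six is mentioned. For the safety criteria, the section refers to Section 8.52.
- **Section 8.1.** The trigger is explicit: "If the mini or full cohort fails either the safety or the PK guidelines". The starting dose is then changed, and "additional new subjects will be enrolled as appropriate at the new dose in order to have a mini-cohort of 6 subjects". Safety and PK are evaluated initially on those children. Children in the failed cohort who were already receiving the newly recommended dose are carried forward.

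Section 8.512, titled "First Six Subjects Started at a Given Dose Level in Each Cohort", makes further accrual depend on a six-child safety rule. The rule fails if any child has a life-threatening suspected adverse drug reaction (SADR), or a death or Grade 4 event probably or definitely due to study drug, or if three or more of the six stop study drug for a Grade 3+ SADR. Section 8.513 applies a 25% limit to everyone started at the dose.

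On children moved from a failed dose to the new one, Section 3.3 (failed mini-cohorts) says they get a three-sample PK, "but will not be considered towards the cohort pass/fail criteria". Section 3.4 gives such children the same three-sample PK but does not repeat the exclusion.

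**The concern.** The two sections prescribe different steps for the same event. Section 3.4 is the more likely one to be followed: Section 6.2 sends readers to Section 3.0 for the review process and dose modifications of mini and full cohorts, and Section 9.351 does the same for handling a revised starting dose. The safety reference in Section 3.4 leads to Section 8.52, which holds the single-event suspension (8.521), and not to Section 8.51, which holds the six-child and full-cohort rules.

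A team that works only from Section 3.4 would therefore lose two planned checks on a new dose: the PK review at six, and the stop for three or more discontinuations in six. The PK review matters because Section 8.1 moves the dose upward when PK is inadequate. The stop matters because it is the only numerical rule that acts on non-life-threatening toxicity before 12 children are on the dose. Section 10.1 cites the sequential cohorts and mini-cohorts as reducing risk to participants.

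The silence of Section 3.4 on switched children adds a second ambiguity, because its words about enrolling only if needed, to a total of 12, come straight after the sentence on adjusting doses for children already in the cohort.

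**Working it through.** **1. Reproduce the plan's own figure.** Let p be the true rate of non-life-threatening SADRs that lead to discontinuation, and q the rate of life-threatening or attributable Grade 4 events, as in Table 8. The six-child rule passes with no q-type event and at most two discontinuations:

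P(fail at six) = 1 − Σ(k=0..2) C(6,k) p^k (1−p−q)^(6−k)

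At p = 0.50, q = 0.05: 0.45^6 + 6(0.50)(0.45^5) + 15(0.25)(0.45^4) = 0.0083 + 0.0554 + 0.1538 = 0.2174, so P(fail) = 0.783. Section 8.512 states 78%. All 11 rows of Table 8 reproduce within two percentage points (largest gap 0.656 against 0.67).

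**2. Take out what Section 8.521 catches anyway.** That section suspends accrual after one qualifying event, whichever section the team is following. With q = 0.05, the chance of at least one such event in six children is 1 − 0.95^6 = 0.265. What remains is failure on discontinuations alone:

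P(≥3 discontinuations, no q-type event) = (1−q)^6 − Σ(k=0..2) C(6,k) p^k (1−p−q)^(6−k)

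At 0.50/0.05 this is 0.7351 − 0.2174 = 0.518.

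**3. Convert to children.** If the trigger at six is omitted and accrual otherwise runs on, up to six more children start the dose before the review.

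| p / q | Table 8 | P(fail at six) | Also caught by 8.521 | Discontinuations only | × 6 |
|---|---|---|---|---|---|
| 0.25 / 0.05 | 0.41 | 0.405 | 0.265 | 0.140 | 0.8 |
| 0.25 / 0 | 0.17 | 0.169 | 0 | 0.169 | 1.0 |
| 0.50 / 0.05 | 0.78 | 0.783 | 0.265 | 0.518 | 3.1 |
| 0.50 / 0 | 0.67 | 0.656 | 0 | 0.656 | 3.9 |
| 0.05 / 0 | 0.002 | 0.002 | 0 | 0.002 | 0.01 |

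**4. Effect on the final decision.** With 12 children, the 25% limit in Section 8.513 allows three discontinuations. P(fail) under the 12-child rule alone is one minus Σ(k=0..3) C(12,k) p^k (1−p−q)^(12−k). The two-step version also requires at most two discontinuations in the first six.

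| p / q | 12-child rule alone | Six, then 12 |
|---|---|---|
| 0.25 / 0.05 | 0.672 | 0.684 |
| 0.25 / 0 | 0.351 | 0.375 |
| 0.50 / 0.05 | 0.973 | 0.974 |
| 0.50 / 0 | 0.927 | 0.932 |

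Skipping the six-child step therefore means more children exposed before review, not a materially weaker final test.

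**5. Switched children: the relevant sections side by side.**

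- Section 3.4 neither counts nor excludes them, but refers back to the text above, which is Section 3.3 with its exclusion.
- Section 8.513 uses children started at the dose. Sections 3.0 and 5.0 want at least 12 per cohort whose first dose was the final one.
- The PK criterion is the 12-hour AUC by the linear trapezoidal rule (Section 9.33). Switched children are sampled pre-dose, at 2 hours and at 3–5 hours, which leaves at least 12 − 5 = 7 hours unobserved. The AUC as defined cannot be computed from those samples.

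**The case against.** The strongest reply is that the safeguard is not missing from the protocol. Section 8.512 applies to any dose level and has no exception for a dose reached after a full-cohort failure. Section 8.513 requires a core-team review after a full-cohort safety failure, Section 8.521 stops accrual after one serious event, and the team reviews data at least twice a month during dose finding (Section 8.5). The gap opens only if a cohort passes at six, then fails in full, and the team reads Section 3.4 without Sections 8.1 and 8.512. The rates that give 3 to 4 extra children are also severe. In the trial of children aged 6 to 17, adverse events led to discontinuation in 2 of 41 children under 12 (4.9%), and at Table 8's 5%/0% row the gain is about 0.01 child.

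All of this stands, and it limits the size of the point. It does not remove the conflict: the regular calls carry no pass/fail rule, and Section 3.4 does not lead the reader to the rule at six.

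Three stronger readings are tempting, and the documents do not support them.

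- *A new dose could reach 12 children with no formal check.* Sections 8.512 and 8.521 still apply.
- *Section 3.4 lets switched children make up the 12, so a dose could be accepted on children who had already tolerated the drug.* Sections 3.3, 8.513, 3.0 and 5.0 point the other way. The phrase about enrolling only if needed has an ordinary explanation: under weight-band dosing, some children may already be on the new dose and are carried forward.
- *The exposure cost is the whole six-child failure probability times six, 2.4 children at 25%/5% and 4.7 at 50%/5%.* That credits the six-child rule with events that Section 8.521 catches.

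**Conclusion.** Sections 3.4 and 8.1 contradict each other on what follows a full-cohort failure. A team following Section 3.4 alone would omit the PK review at six and the trigger of three or more discontinuations in six. The omitted trigger corresponds to up to about 0.8 (25%/5%), 1.0 (25%/0%), 3.1 (50%/5%) or 3.9 (50%/0%) more children exposed before review, with almost no change in the 12-child verdict.

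These figures rest on Table 8's hypothetical rates, on all 12 children being newly started at the new dose, and on accrual running to 12 unless the six-child rule intervenes. They are upper figures, because a team call, or a Section 8.521 suspension among children 7 to 12, could halt accrual sooner, and carried-forward children reduce the number newly exposed. The lost PK review has no such figure, but it belongs to the same step.

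On switched children, Section 3.4 is silent where it should be explicit. The rest of the protocol indicates that they do not count. The SAP text does not settle either question. Protocol Figure 2, the cohort algorithm, could not be read in the text available and should be checked against whatever wording is adopted.

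**What to change.** Reconcile Section 3.4 with Sections 8.1, 8.512 and 8.513, in one paragraph:

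1. State that after a full-cohort failure, the six-child evaluation already required by Section 8.1 comes before filling to 12. The six may include children carried forward because they were already on that same dose.
2. State, consistently with Sections 3.3 and 8.513, that children switched from the failed dose do not count towards the cohort PK or safety criteria.
3. Extend the safety cross-reference in Section 3.4 from 8.52 to include 8.512 and 8.513. Section 3.3 carries the same reference to 8.52 and needs the same correction.

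The cost is a text amendment, one pause at six if a full cohort fails, and perhaps a few more newly started children than a literal reading of Section 3.4 would need. Sections 8.1 and 8.513 already imply those children. If six or more children are carried forward, the evaluation at six can use data already in hand.
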